## STUDY ENDPOINTS:

### Primary endpoints

The primary endpoints of this proposal are the analysis of neural representations of high-caloric food odors in early olfactory cortex and food reward regions, and levels of orexigenic hormones using the serial blood samples.

### Secondary endpoints

Secondary endpoints of this proposal are the total calories of food consumed during the ad-libitum food intake phase, subjective ratings of hunger, fullness, prospective food consumption, and satiety using the visual analogue scale, food craving questionnaire, and total calorie intake using the self-reported food intake for 24 h following the fMRI scan.

## PROCEDURES INVOLVED:

We propose to implement a randomized within-subject, crossover partial sleep-deprivation protocol to examine the effects of sleep deprivation (SD) on neural processing of food odors in early sensory and reward-related brain regions. In brief, after a one-week sleep stabilization period, subjects will spend a night either sleep deprived (SD, 4 h of sleep) or with normal sleep (non-SD, NDS, 8 h of sleep) at home. On the next day, fMRI scanning will be conducted at 7 pm after dinner, when sleep-deprivation induced changes in hormonal levels are most prominent (11). Hormone levels will be monitored using serial blood sampling in response to a meal (dinner).

**Sleep-deprivation protocol.** Subjects (N=40) will be randomly assigned to either participate in the SD or the NSD condition first (**Fig. 2A**). Subjects will then undergo a sleep stabilization phase to stabilize circadian rhythms. During this week, subjects will be instructed to keep a regular sleep schedule of 7-9 hours in bed between 10:30 pm and 7:30 am. Participants will abstain from alcohol, caffeine, and drugs in this phase. After the sleep stabilization week, the night before the fMRI session, subjects will either sleep normally (NSD, 8 h of sleep between 11 pm and 7 am), or sleep only for 4 h between 1 am and 5 am (SD) at home. We opted for a partial sleep-deprivation protocol because this situation (late bedtime and early wakeup) is ecologically valid as it reflects the most realistic form of sleep-deprivation in

everyday life. All subjects will participate in both sleep conditions (SD and NSD) in randomized order, separated by a 2.5-week washout period.

*Sleep-monitoring.* To ensure that subjects follow the sleep schedule during the sleep stabilization phase and sleep manipulation days, we will record sleep duration, as well as sleep and wake-up time using a daily sleep diary and wrist actigraphy (ActiGraph, LLC, Pensacola, Florida (45)). Additionally, subjects will rate their subjective sleep quality, alertness, and restfulness every morning using an online questionnaire. Subjects will also rate their subjective sleepiness using the Stanford Sleepiness Scale (46) before the fMRI scan during both the SD and NSD phase. Participants will spend the night of sleep manipulation (both SD and NSD) at home and food will be provided for these days.

*Controlled diet protocol.* During the 24 h before the fMRI session, we will provide subjects with a controlled diet based on their estimated energy requirements. Specifically, the evening of the sleep manipulation, subjects will consume dinner at 7 pm at our lab and will also be provided with a take-out breakfast and lunch to be consumed at 8:00 am and 12:00 noon the next day. No other calorie intake will be permitted. Participants will be instructed to consume only non-caffeinated and non-caloric drinks.

*fMRI scanning protocol.* On the first day of the study, before being assigned to the SD or NSD phase, subjects will rate the pleasantness of six food odors, including three high caloric sweet (caramel, yellow cake, ginger bread) and three high caloric savory odors (potato chips, pot roast, garlic butter). Based on each participant's ratings, we will select two sweet and two savory odors matched in rated pleasantness. We will also include two control non-food odors (fir and celery seed). On the day of fMRI scanning, subjects will arrive at the imaging center at 6 pm and will consume a dinner before entering the scanner. This pre-feeding will satisfy metabolic hunger (i.e., energy requirements), and thus render the fMRI measures more sensitive to sleep-dependent changes in hedonic hunger, i.e., food intake exceeding energy requirements (47). During fMRI data acquisition, odors will be delivered directly to the subject's nose via a MR-compatible olfactometer. Neuroimaging will be performed at the Northwestern University Center for Translational Imaging (CTI) on a state-of-the-art Siemens PRISMA system with a 64 channel head coil, using imaging sequences optimized for signal recovery in olfactory and orbitofrontal cortices (48). Specifically, subjects will perform 4 runs of an odor detection task inside the MRI scanner while blood oxygen-level dependent (BOLD) responses will be acquired with high spatial (2 mm isotropic) and temporal resolution (2000 ms). On each trial, subjects will be cued to sniff, and an odor corresponding to one of the three experimental groups (sweet, savory, non-food) or clean air will be delivered pseudo-randomly. Subsequently, subjects will rate the pleasantness or the intensity (pseudo-randomized) of the delivered odor. Sniffing behavior will be monitored using an MR-compatible breathing belt and a spirometer. A high-resolution anatomical image will be acquired for the purpose of spatial normalization and anatomical localization of the fMRI responses.

*Hormone levels.* As soon as subjects arrive at the imaging center, an intravenous sterile heparin-lock catheter will be inserted in a forearm vein and blood sampling will be initiated by the CRU mobile nurse. We will draw blood every 30 min after arrival, resulting in 5 samples, including a fasted baseline (6 pm), after dinner (6:30 pm), before (7 pm), during (7:30 pm, after the second scanning run), and after the scanning session (8 pm) for leptin and ghrelin analysis. An additional sample will be collected at 7:30 pm time point for 2-AG and 2-OG analysis. Plasma and serum samples will be frozen at  $-80^{\circ}\text{C}$  until assay for ghrelin, leptin, insulin using commercially available ELISA kits, and 2-AG and 2-OG using published procedures (49, 50). Phase of menstrual cycle in women has an impact on these hormonal levels. The 2.5-week washout period will ensure that the blood samples are collected in the same phase of the menstrual cycle

*Ad-libitum food intake.* At the completion of the fMRI scan, participants will be provided with snacks in a

buffet-style setting where they will have *ad libitum* access to food items corresponding to the odors used during fMRI scanning (sweet and savory high-calorie snacks). They will be instructed to consume as much food as they like. To measure food intake, food will be weighed pre- and post- consumption, and calories consumed will be calculated. Because subjects have been provided with dinner before the scanning session, food intake at the buffet will mainly reflect hedonic, rather than metabolic eating (47). *Appetite and hunger ratings.* Subjective food craving, ratings of hunger, fullness, prospective food consumption, and satiety will be measured using a visual analogue scale. These ratings will be acquired on the fMRI scanning day upon arrival, at all blood collection time points, and after the *ad libitum* meal. Subjects will also complete the food craving questionnaire on the day of fMRI scan.

*24 h post-fMRI food intake diary.* Subjects will be instructed to carefully record the food items, quantity consumed, place of consumption, and the food brands, for 24 h following the fMRI scan. We will calculate the total energy, fat and carbohydrate consumption for SD and NSD states.

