**MULTI-SITE RESEARCH: N/A**

**STUDY TIMELINES:**

Each participant will follow a ~ 6 week within-subject, crossover partial sleep-deprivation protocol to test the effect of sleep deprivation (SD) and non-sleep deprivation (NSD) on neural processing of food odors in sensory and reward related regions (**Fig. 2**). Qualified subjects will be randomly assigned to either participate in the SD or the NSD condition first. Subjects will then undergo a week of sleep stabilization phase to stabilize circadian rhythms for a week. After the sleep stabilization week, the night before the fMRI session, subjects will either sleep normally (NSD, 8 h of sleep between 11 pm and 7 am), or sleep only for 4 h between 1 am and 5 am (SD) at home. All subjects will participate in both sleep conditions (SD and NSD) in randomized order, separated by ~2.5 week washout period. The

evening of the sleep manipulation, subjects will visit the lab to consume dinner and pick up their sleep monitors. We will also provide a take-out breakfast and lunch to be consumed at 8:00 am and 12 noon, respectively. All meals will be provided by the CRU. Subjects will perform an odor-rating task inside the MRI scanner on the same evening. Serial blood samples will be collected for measurement of appetite-regulating hormones. At the completion of the fMRI scan, participants will be provided with snacks in a buffet-style setting where they will have *ad libitum* access to food items corresponding to the odors used during fMRI scanning (sweet and savory high-calorie snacks). They will be instructed to consume as much food as they like. We anticipate to enroll all participants within a 12-month period and plan to complete the study data collection and analyses within a period of 3 years from the date of IRB approval.

**Figure 2. Study design and scanning protocol. A.** Timeline of the sleep-deprivation protocol. All subjects will participate in both sleep conditions (SD and ND), in randomized order. On the scanning day, blood (BD) will be drawn every 30 min. **B.** For each subject, two sweet and two savory high-calorie food odors will be selected and presented during the scanning session, in addition to two non-food odors and trials in which non-odorized air is presented. **C.** Example trial of the fMRI task. After a countdown, an odor is presented, after which subjects have to rate the pleasantness or the intensity of the delivered odor.

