#### **DATA AND SPECIMEN MANAGEMENT:**

Sample size is based upon the requirements for group analysis, particularly when random-effects analyses are performed. Random-effects analyses require a minimum of 14 -18 subjects in each group in order to obtain statistically meaningful fMRI effects. Our target subject number also accounts for attrition in the subject pool due to unanticipated claustrophobia, technical/mechanical issues, or other problems during the fMRI session.

For the statistical analyses, comparisons of subjective appetite ratings and calorie intake between the SD and NSD state will be carried out using paired t-tests. Spearman's correlation analysis will be used to test the relation between appetite ratings, neural responses to food odors, and the total calories consumed. Moreover, we will use whole-brain mediation analysis (51) to identify the brain regions in which neural responses to food odors mediate the link between sleep-dependent changes in hormone levels and enhanced calorie intake. To identify brain mechanisms related to resilience, we will compare fMRI responses to food odors between subjects that manage to abstain from excess calorie intake in a sleep-deprived state to those that do not. We will use fMRI connectivity analyses (psychophysiological interaction, PPI (52)) to test the hypothesis that resilience to enhanced food intake in a SD state is associated with enhanced functional connectivity between the dorsolateral prefrontal cortex and reward-related brain regions (53). We will monitor sniffing using a breathing belt and spirometer, and model trial-by-trial sniff parameters will be included as covariates in all fMRI analyses following established procedures to control for respiration-induced effects.

To preserve subject privacy and confidentiality, all research materials (questionnaires, behavioral testing results, and magnetic resonance imaging data) will be coded by a different study code number unique for each subject, in order to keep the identity and personal information of each subject as confidential as possible. This number will be recorded on all testing sheets instead of the subject's

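### The 2.5-week washout cannot guarantee same-phase blood draws: no single interval matches menstrual phase across cycle lengths, and the visible text has no other control on phase

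*Protocol*

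**What the plan says.** The Hormone levels paragraph of the Protocol (Procedures Involved) gives the premise, "Phase of menstrual cycle in women has an impact on these hormonal levels", and then the control: "The 2.5-week washout period will ensure that the blood samples are collected in the same phase of the menstrual cycle". Orexigenic hormones are part of the primary endpoint: "levels of orexigenic hormones using the serial blood samples". The recruitment section expects equal numbers of men and women.

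On timing, Study Timelines has the conditions "in randomized order, separated by ~2.5 week washout period", and Procedures Involved has them "in randomized order, separated by a 2.5-week washout period". Procedures Involved also says that "after a one-week sleep stabilization period, subjects will spend a night either sleep deprived". It does not say whether that week is repeated before the second session, or whether a repeat would fall inside the washout or after it. Study Timelines gives a total: "Each participant will follow a ~ 6 week within-subject, crossover partial sleep-deprivation protocol".

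The SAP (Analysis of hormones) expresses each hormone as percentage change from the non-deprived session and tests it against zero with a one-sample t-test. It has no phase term. In Data and Specimen Management, the Protocol also plans a mediation analysis for regions that "mediate the link between sleep-dependent changes in hormone levels and enhanced calorie intake".

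**The concern.** The Protocol names a source of variation in a primary endpoint and offers one device to remove it. A reader would conclude that phase had been controlled. One interval in days can return every woman to the same cycle day only if all cycles have the same length. Nothing else in the visible text does the job: there is no eligibility rule on cycle length, regularity or hormonal contraception, no booking by cycle day, no cycle record and no analysis that uses phase.

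At stake are the precision of the hormone comparison in about half the sample and the strength of the individual-level hormone associations that the mediation analysis depends on.

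**Working it through.** **Inputs from the documents.** Washout 2.5 x 7 = 17.5 days. Stabilisation 7 days. Manipulation night to scan 1 day. Food diary after the scan 1 day. Enrolment 40, drop-out 15-25%, half women: 40 x 0.75 to 40 x 0.85 = 30-34 completers, so 15-17 women.

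**Assumptions, not in the documents.** Cycle length L of 24-35 days, a 14-day luteal phase, a random cycle day at the first draw, and every woman cycling naturally.

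**1. The plan's own duration.** Participation = 7 + 1 + draw-to-draw interval + 1.
- Washout is the whole separation (17.5 days): 26.5 days, or 3.8 weeks.
- Second stabilisation week after the washout (17.5 + 7 = 24.5 days, or 25.5 with the manipulation night): 33.5-34.5 days, or 4.8-4.9 weeks.

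Neither sum by itself reaches about six weeks, so the stated total does not show which interval is meant.

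**2. Phase offset.** For interval g, d = min(g mod L, L - g mod L), in days:

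| g | L = 24 | L = 28 | L = 32 | L = 35 |
|---|---|---|---|---|
| 17.5 | 6.5 | 10.5 | 14.5 | 17.5 |
| 24.5 | 0.5 | 3.5 | 7.5 | 10.5 |
| 25.5 | 1.5 | 2.5 | 6.5 | 9.5 |

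The single interval with the smallest worst-case offset over L = 24-35 is 29.5 days. It still leaves 35 - 29.5 = 5.5 and 29.5 - 24 = 5.5 days at the two ends. That figure shows the limit of any fixed interval; it is not a proposal.

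**3. Chance that the two draws fall in different phases.** With two phases of 14 and L - 14 days, p = 2 x min(d, 14, L - 14) / L.
- L = 28: 2 x 10.5/28 = 0.75 at 17.5 days; 2 x 3.5/28 = 0.25 at 24.5; 2 x 2.5/28 = 0.18 at 25.5.
- L = 35: 2 x 10.5/35 = 0.60 at 24.5 days; 2 x 9.5/35 = 0.54 at 25.5.
- Equal weight on whole-day lengths 24-35: 0.758 at 17.5 days, 0.323 at 24.5, 0.274 at 25.5.

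The averages correspond to 0.274 x 15 = 4.1 up to 0.323 x 17 = 5.5 women at 24.5-25.5 days, and 0.758 x 15 = 11.4 up to 0.758 x 17 = 12.9 women at 17.5 days. These are upper bounds, because hormonal contraception is not excluded.

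**4. Effect on spread, illustration only.** The documents give neither the size of the phase difference (a) nor the SD of the percentage change (s). With half the sample women, whole-sample SD ratio = sqrt(1 + 0.5 x p x a²/s²). For a = 10-30% and s = 20-30%, with L = 28:
- 24.5-25.5 days: from sqrt(1 + 0.5 x 0.179 x 0.111) = 1.005 to sqrt(1 + 0.5 x 0.25 x 2.25) = 1.13.
- 17.5 days: from sqrt(1 + 0.5 x 0.75 x 0.111) = 1.02 to sqrt(1 + 0.5 x 0.75 x 2.25) = 1.36.

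The upper ends need a phase difference 1.5 times the SD (30% against 20%).

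**5. Effect on associations.** Correlations with hormone change shrink by 1/(SD ratio). At 24.5-25.5 days averaged over L = 24-35, with a = s = 20%: 1/sqrt(1 + 0.5 x 0.323) = 0.93 to 1/sqrt(1 + 0.5 x 0.274) = 0.94. Over the full assumed range of a and s it is 0.86-0.99.

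**6. Effect on the mean.** Randomised order makes upward and downward phase shifts equally likely. A percentage change is slightly asymmetric: with a = 20%, shifts of +20% and 1/1.2 - 1 = -16.7% average +1.67%. Times 0.5 x 0.274 to 0.5 x 0.323, this is 0.2-0.3 percentage points.

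**The case against.** The best defence is that the control largely works under the reading that Procedures Involved suggests. At 24.5-25.5 days, a woman with a 28-day cycle is 2.5-3.5 days off and has a 75-82% chance of staying in the same phase. The approximate sign in Study Timelines leaves room to move a visit by a few days. This stands: phase matching is not ensured, but it would be wrong to say that the washout achieves nothing.

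A reader might infer that the six-week total contradicts the washout, or that draws could be 33 days apart (42 - 7 - 1 - 1). The documents do not support either as a finding. The 33 days is an outer bound that puts all unplaced time between the scans. The Protocol mentions a week to decide on consent and a week of recovery sleep. Added to 34.5 days, these would give 41.5 days (5.9 weeks) or, with the diary day inside the recovery week, 40.5 days (5.8 weeks). The text does not say whether either week counts. Figure 2A, which shows the timeline, may also fix the interval.

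A reader might also infer that the primary hormone comparison is biased or that the mediation result could be spurious. Randomised order removes material bias in the mean, and the one-sample t-test uses the observed variance. A false hormone-intake link would need phase also to shift intake or neural response, which the documents do not state. The SAP's analysis sections do not describe the mediation analysis, so attenuation concerns the Protocol's plan.

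Finally, the SAP is in the past tense. If collection is complete, booking by cycle day is no longer possible.

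**Conclusion.** The point holds in a limited form. The stated guarantee of same-phase sampling is wrong for any fixed interval, whatever Figure 2A shows, and the visible text has no second control. This needs only the fact that cycle lengths differ. The particular offsets rest on the assumed lengths.

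The consequence is lost precision in women's hormone changes and attenuated hormone associations. Its size cannot be determined from the documents, because they give no phase amplitude, hormone variance or contraceptive use. Under the assumptions shown, the loss is small at 24.5-25.5 days with 28-day cycles unless the phase difference exceeds the SD of the change. It is larger with longer cycles or with the literal 17.5 days. The primary hormone test remains valid.

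**What to change.** - Replace the guarantee in the Hormone levels paragraph with wording that does not claim phase matching. State the scan-to-scan interval in days, consistently there, in Study Timelines and in the sleep-deprivation protocol.
- At each session, record date of last menses, usual cycle length and hormonal contraceptive use. Book each woman's second session by her own cycle day where the approximate washout allows.
- Keep the full-sample hormone test primary. Add one sensitivity analysis: the SAP's one-sample t-tests repeated in men plus phase-matched women, with a cycle-day tolerance set beforehand.
- If the data are already collected, report the actual scan-to-scan intervals and any cycle data held, run the same check where possible, and state unmatched phase as a limitation. Without cycle data, a men-only analysis is a low-precision robustness check. At equal SD, its confidence interval is [t(0.975, 14)/sqrt(15)] / [t(0.975, 29)/sqrt(30)] = 1.48 times as wide for 15 of 30 completers, and 1.47 times for 17 of 34.

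The cost is three self-report questions, a wording change and one repeat of planned tests. Some second visits would shift by days and must still fit evening scanner and nurse slots. The sensitivity sample is smaller than the full one and does not replace it.

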#### **DATA AND SPECIMEN BANKING:**

Once the blood samples are obtained, we will store them in a freezer in the lab at -80 Celcius until assay. Blood samples will be sent to the Comprehensive Metabolic Core lab at the Northwestern University for hormone analyses. Blood samples will also be sent to the lab of [name] at the Medical College of Wisconsin, Milwaukee for endocannabinoid analysis. These labs will be instructed to destroy the samples immediately once the desired data is obtained. All samples will be labeled with the subject study codes and date of collection. The lab technicians of the lab where the samples will be sent will be completely blinded to the purpose of the sample collection. The lab results will be returned to the research personnel with the subject codes who will then enter the raw data in the study spreadsheet. Lab technicians will not have access to the spreadsheet and will not be able to identify subjects. Only research personnel included in the IRB application will have access to the raw data.

#### **DATA AND SPECIMEN MANAGEMENT:**

Sample size is based upon the requirements for group analysis, particularly when random-effects analyses are performed. Random-effects analyses require a minimum of 14 -18 subjects in each group in order to obtain statistically meaningful fMRI effects. Our target subject number also accounts for attrition in the subject pool due to unanticipated claustrophobia, technical/mechanical issues, or other problems during the fMRI session.

For the statistical analyses, comparisons of subjective appetite ratings and calorie intake between the SD and NSD state will be carried out using paired t-tests. Spearman's correlation analysis will be used to test the relation between appetite ratings, neural responses to food odors, and the total calories consumed. Moreover, we will use whole-brain mediation analysis (51) to identify the brain regions in which neural responses to food odors mediate the link between sleep-dependent changes in hormone levels and enhanced calorie intake. To identify brain mechanisms related to resilience, we will compare fMRI responses to food odors between subjects that manage to abstain from excess calorie intake in a sleep-deprived state to those that do not. We will use fMRI connectivity analyses (psychophysiological interaction, PPI (52)) to test the hypothesis that resilience to enhanced food intake in a SD state is associated with enhanced functional connectivity between the dorsolateral prefrontal cortex and reward-related brain regions (53). We will monitor sniffing using a breathing belt and spirometer, and model trial-by-trial sniff parameters will be included as covariates in all fMRI analyses following established procedures to control for respiration-induced effects.

To preserve subject privacy and confidentiality, all research materials (questionnaires, behavioral testing results, and magnetic resonance imaging data) will be coded by a different study code number unique for each subject, in order to keep the identity and personal information of each subject as confidential as possible. This number will be recorded on all testing sheets instead of the subject's

name. In addition, if the individual results of this study are used for teaching, research, publications, or presentations at scientific meetings, subject identity will be protected by using the study code number rather than subject name or other identifying information, including (but not limited to) Social Security number, date of birth, or address. In order to secure the data, all paper data will be de-identified and kept in a locked cabinet. The de-identified data will also be entered into spreadsheets and saved in the encrypted form on the password protected University's secure server, protected by the Northwestern's firewall. This dataset will also be stored within password protected folders to which only the PI and study personnel will have access. Only the PI and the key personnel will have access to the identifiable information and the data. All electronic data and records of the individuals who after screening are deemed ineligible for the study will be completely de-identified and destroyed. Finally, unless required by law, only the study investigator, members of the investigator's staff, representatives from the Cognitive Neurology and Alzheimer's Disease Center, and the Northwestern University Institutional Review Board will have the authority to review the study records. They will all be required to maintain the strictest confidentiality regarding subject identity.

As explained above, blood samples will be stored in a freezer in the lab at -80 Celcius until assay. All samples will be labeled with the subject study codes and date of collection. The lab technicians of the lab where the samples will be sent will be completely blinded to the purpose of the sample collection. The lab results will be returned to the research personnel with the subject codes who will then enter the raw data in the study spreadsheet. Lab technicians will not have access to the spreadsheet and will not be able to identify subjects. Only research personnel included in the IRB application will have access to the blood samples and raw data, and will be able to transport the samples to the Comprehensive Metabolic Core lab and the Medical College of Wisconsin lab for hormonal analysis.

